#### 5.3 Subject Selection

##### 5.3.1 Inclusion Criteria:

(1) Clinical diagnosed of NENs.

(2) Suspected of NENs.

##### 5.3.2 Exclusion Criteria:

(1) Inability to undergo biopsy/surgical treatment.

(2) Concurrent active malignancy.

(3) Severe uncontrolled comorbidities/active infections.

(4) Inability to provide informed consent.

#### 5.3.3 Criteria and Procedures for Subject Withdrawal:

Subjects not meeting inclusion criteria (verified via medical history/electronic records) will be excluded. Subjects may withdraw during the procedure due to hypoglycemia, tremor, pain, or severe abdominal discomfort.

#### 5.3.4 Loss to Follow-up:

- Defined as incomplete follow-up without formal withdrawal.
- For subjects receiving biopsy/surgery elsewhere,  $\geq 3$  phone attempts will be made. Unresponsive cases after 3 calls + certified mail will be deemed "lost to follow-up."
- Lost subjects are excluded from diagnostic efficacy analysis but included in safety assessment if data are available.

5.3.5 Enrollment Period: December 2024 to December 2027 (3 years).

5.3.6 Sample Size: 152 cases.

### 5.4 Study Endpoints:

Study completion is defined as completion of multimodal imaging and acquisition of pathological results.

---

## 6. Research Procedures and Protocols

### 6.1 Ethics and Informed Consent

- The study commences after ethics committee (EC) approval. Protocol amendments require re-approval.
- EC approval (including consent forms) must be documented with version/date.

- Written informed consent is mandatory before enrollment.

## 6.2 Subject Screening

- Consent is obtained after explaining risks/benefits. Subjects receive time to consider participation.
- Baseline data (general exams, labs, history from within 1 week pre-consent) are collected. Adverse events/concomitant medications are recorded post-consent.

## 6.3 Medical History Collection

Comprehensive documentation of:

- Symptoms, signs, and history (tumors, surgeries, biopsies, radiotherapy, chemotherapy, allergies, octreotide/PRRT history).
- Lab tests: Fasting insulin, CgA, proinsulin/C-peptide, NSE, VIP, Syn, VMAT-2, CD56.
- Prior imaging (X-ray, US, CT, MRI, 18F-FDG PET/CT/MR).
- Recent pathology (grading, Ki-67 index).

## 6.4 Patient Preparation

Pregnancy: Avoid unless benefits outweigh risks.

Hydration: Encourage water intake pre/post-injection to reduce radiation exposure and improve image quality. Void bladder pre-scan; catheterize if incontinence occurs.

IV Access: Use a cannula to prevent tracer extravasation.

Fasting/Fasting Medications: Not required. Withhold short-acting octreotide  $\geq 24$ h and long-acting analogs 3–4 weeks pre-scan if feasible (evidence inconclusive).

## 6.5 Radiopharmaceutical Administration

- Dose: 18F-Octreotide (3.7 MBq/kg, range 3.7–4.44 MBq; obese patients may receive higher doses).
- Administration: IV injection separate from parenteral nutrition lines.

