## 6.6 Image Acquisition

- Patient Positioning: Arms at sides for whole-body scans; arms raised for chest/abdomen.
- CT Protocol: For attenuation correction/anatomic localization. Use low-dose principles where feasible.
- PET Protocol:

Optimal imaging: 45–60 min post-injection.

Scan range: Skull base to mid-thigh (adjust per clinical needs).

Acquisition time varies by dose, BMI, scanner.

- Interventions: Hydration  $\pm$  diuretics/catheterization to reduce urinary tracer activity.
- Reconstruction: Iterative reconstruction + time-of-flight (if available); parameters optimized per patient/scanner.

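### The dose range in Protocol section 6.5 lacks '/kg' and cannot bound the 3.7 MBq/kg dose printed beside it

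*Protocol*

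**What the plan says.** Section 6.5 of the protocol (Radiopharmaceutical Administration) gives the dose in one line: "18F-Octreotide (3.7 MBq/kg, range 3.7–4.44 MBq; obese patients may receive higher doses". It contains three elements:

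- a weight-based dose of 3.7 MBq/kg;
- a permitted range, printed as "range 3.7–4.44 MBq", with no per-kilogram unit;
- an exception, "obese patients may receive higher doses", with no amount attached.

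No other section states an administered activity. Section 3.2 lists quality specifications of the product, not a patient dose. Section 6.6 mentions dose only as a factor in scan duration ("Acquisition time varies by dose, BMI, scanner"). Section 6.8 lists the injection as a step in the procedure without an amount.

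**The concern.** A dose in MBq/kg and a range in MBq are different quantities. The first scales with body weight and the second does not. A range printed directly after a dose should tell staff and monitors how far the administered activity may depart from it, and here it cannot.

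Read literally, the line allows two outcomes. Either every adult dosed correctly at 3.7 MBq/kg is a protocol deviation, or staff keep to the range and give a small fraction of the intended activity. If the range is ignored instead, no stated upper limit remains for patients who are not obese. Sections 16–18 make the sponsor responsible for protocol adherence and data auditing, and the printed range gives no usable standard for that check.

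**Working it through.** **Inputs**

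- Dose: 3.7 MBq/kg (section 6.5).
- Range as printed: 3.7–4.44 MBq (section 6.5).
- Body weight: the protocol gives none. Weights of 40–100 kg are assumed for illustration.

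**Step 1. Can the dose fall inside the printed range?**

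Total activity = 3.7 MBq/kg × weight. Setting this equal to the two ends of the range gives

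- lower end: 3.7 / 3.7 = 1.0 kg
- upper end: 4.44 / 3.7 = 1.2 kg

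The two figures agree only for a body weight of 1.0–1.2 kg. This result needs no assumption about weight.

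**Step 2. How far apart are they at adult weights, and does '/kg' repair the line?**

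| Weight (assumed) | Dose at 3.7 MBq/kg | Dose ÷ 4.44 MBq | Range if read as 3.7–4.44 MBq/kg |
|---|---|---|---|
| 40 kg | 148 MBq | 33.3 | 148–177.6 MBq |
| 50 kg | 185 MBq | 41.7 | 185–222 MBq |
| 60 kg | 222 MBq | 50.0 | 222–266.4 MBq |
| 70 kg | 259 MBq | 58.3 | 259–310.8 MBq |
| 80 kg | 296 MBq | 66.7 | 296–355.2 MBq |
| 100 kg | 370 MBq | 83.3 | 370–444 MBq |

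As printed, the prescribed dose is 33 to 83 times the upper limit over these weights. With '/kg' added, it sits at the lower end of the range at every weight.

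**Step 3. Is a dropped unit the likely cause?**

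The range opens with the same number as the dose, and its upper end is 4.44 / 3.7 = 1.2 times that number, so it reads naturally as the dose plus 20%. The obese-patient clause points the same way. As an exception it makes sense only if other patients can stay within the range, and under the printed unit no adult does.

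**Step 4. Could the unit have been lost when the PDF was read?**

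This cannot be fully excluded. However, '/kg' is intact a few words earlier in the same line, the line is plain prose rather than a table or formula, and nothing in it is marked as removed.

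**The case against.** The strongest reply is that the line resolves itself. The governing unit comes first, the range starts at the same number, and only one reading makes sense. On that reading there is no discrepancy, and the factor of 58 measures an interpretation that no one would act on. The weight-based dose itself is printed correctly and remains an auditable target. The protocol defines no specific dose-deviation check that uses the range. Sections 16–18 also require training in radiopharmaceutical handling before the study starts. On this view the slip is an editorial omission of a unit, not a miscalculation.

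Much of this stands. The intended meaning is easy to infer, the practical risk is low, and no computed quantity in the plan is wrong. The factor of 58 shows that the printed range cannot apply. It does not estimate a likely dosing error.

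The objection does not make the line correct. A limit on administered radioactivity should not depend on the reader supplying its unit, and no other section supplies it. What is lost is the stated upper tolerance for patients who are not obese, and that is the part an adherence check would need.

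**Conclusion.** The concern holds. The range in section 6.5 is wrong as printed for every adult, since it agrees with the dose beside it only at 1.0–1.2 kg. At an assumed 70 kg, the dose of 259 MBq is 58 times the printed upper limit. The weights are illustrative, and the conclusion is the same for any adult weight.

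That '/kg' was dropped is an inference, though a strong one. It rests on the shared 3.7, the ratio of 1.2 and the fit of the per-kilogram reading. The finding also assumes that the text at hand matches the sponsor's page.

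The defect should be fixed because it lies in the only dosing limit for a radioactive agent. It has no bearing on the endpoint, the sample size of 152 or the planned analyses.

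**What to change.** Check the source page, and have the sponsor confirm the range against its own dosing instruction. Then amend section 6.5 to give the dose as 3.7 MBq/kg with a range of 3.7–4.44 MBq/kg. Keep the allowance for obese patients as the express exception it already is, and use the corrected range when checking for dose deviations.

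The cost is a one-line amendment. Section 6.1 requires ethics re-approval for amendments, so it can sensibly travel with the next one if that is near. Sample size, procedures and analysis do not change.

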## 6.6 Image Acquisition

- Patient Positioning: Arms at sides for whole-body scans; arms raised for chest/abdomen.
- CT Protocol: For attenuation correction/anatomic localization. Use low-dose principles where feasible.
- PET Protocol:

Optimal imaging: 45–60 min post-injection.

Scan range: Skull base to mid-thigh (adjust per clinical needs).

Acquisition time varies by dose, BMI, scanner.

- Interventions: Hydration  $\pm$  diuretics/catheterization to reduce urinary tracer activity.
- Reconstruction: Iterative reconstruction + time-of-flight (if available); parameters optimized per patient/scanner.

## 6.7 Image Interpretation

- Normal Biodistribution: Spleen (highest), kidneys, liver, adrenals, pituitary, salivary glands. Minimal uptake in brain/lungs/muscle; excreted via kidneys.
- Pathologic Uptake: Focal uptake in non-physiologic sites (vs. diffuse bowel uptake = non-pathologic).
- Malignancy Criteria: Uptake  $>$  liver = SSTR-positive malignancy. Correlates with tumor grade/SSTR expression.

## 6.8 Reporting Standards

Objectives: Address referring physicians' clinical queries and justify necessity/diagnostic value of  $\text{^{18}F}$ -Octreotide imaging.

Procedure Flow:

Registration → 2. Preparation (fast  $\geq 4$ h) → 3. History/consent → 4.  $\text{^{18}F}$ -Octreotide injection → 5. Uptake period (60 min) → 6. Scan (20–30 min).

## 7 Statistical Considerations

### 7.1 Total Sample Size

Assuming a sensitivity of 0.90, specificity of 0.88, and disease prevalence of 0.25 from literature, with a margin of error of 0.1 and  $\alpha = 0.05$ :

For sensitivity calculation:

$$( N_1 = \frac{1.96^2 \times 0.9 \times (1-0.9)}{0.1^2 \times 0.25} = 138 )$$

For specificity calculation:

$$( N_2 = \frac{1.96^2 \times 0.88 \times (1-0.88)}{0.1^2 \times (1-0.25)} = 54 )$$

The theoretical sample size is estimated at 138 cases. Accounting for a 10% expected dropout rate (based on prior studies), the adjusted total sample size is 152 cases.

### 7.2 Significance Level and Power

Significance level:  $\alpha = 0.05$

Power: 0.95

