### 7.3 Statistical Methods

Analysis performed using SPSS 17.0:

Sensitivity, specificity, and positive/negative predictive values calculated via  $2 \times 2$  contingency tables.

ROC curves used to determine AUC and optimal cut-off values (e.g., SUV thresholds).

Kappa test evaluated consistency between 18F-Octreotide PET/CT and pathological diagnoses.

Statistical significance:  $p < 0.05$ .

---

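### Section 7.2 states a power of 0.95 that belongs to no hypothesis: the sample size in 7.1 is a precision calculation, so the power is undefined

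*Protocol*

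**What the plan says.** Protocol section 7.1 sets out its inputs: "Assuming a sensitivity of 0.90, specificity of 0.88, and disease prevalence of 0.25 from literature", "with a margin of error of 0.1 and" a two-sided alpha of 0.05 (multiplier 1.96). Sensitivity governs, since specificity needs only 54: "The theoretical sample size is estimated at 138 cases". The total is then raised for loss: "Accounting for a 10% expected dropout rate (based on prior studies), the adjusted total sample size is 152 cases".

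The next section, headed "7.2 Significance Level and Power", consists of two figures, an alpha of 0.05 and a power of 0.95. It names no test, null value, comparator or performance goal.

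Section 7.3 plans estimates ("Sensitivity, specificity, and positive/negative predictive values calculated via" two-by-two tables), ROC curves with cut-off selection, and one named test: "Kappa test evaluated consistency between 18F-Octreotide PET/CT and pathological diagnoses". A threshold of p<0.05 is given in general terms. Section 5.4 defines the endpoint as completing the imaging and obtaining pathology. Section 5.3.4 removes subjects lost to follow-up from the diagnostic efficacy analysis.

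**The concern.** Power is the probability of rejecting a stated null hypothesis under a stated alternative. A calculation that fixes only the width of a confidence interval has neither, so no power follows from it. A figure of 0.95 placed directly after the sample size will be read as a result of that calculation, and an ethics committee or later reader may credit the study with an assurance that nobody derived.

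A second question is whether the total of 152 covers the stated 10% loss, given that lost subjects leave the efficacy analysis.

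**Working it through.** **Inputs, all from section 7.1 unless noted.** Sensitivity 0.90, specificity 0.88, prevalence 0.25, half-width d = 0.10, multiplier 1.96, loss 10%. Power 0.95 is from 7.2.

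**Step 1: reproduce the plan's sample size.**
- Sensitivity: N1 = 1.96² x 0.90 x 0.10 / (0.10² x 0.25) = 0.345744 / 0.0025 = 138.30. Stated: 138.
- Specificity: N2 = 1.96² x 0.88 x 0.12 / (0.10² x 0.75) = 0.405673 / 0.0075 = 54.09. Stated: 54.
- Inflation: 138 x 1.10 = 151.8, so 152. Stated: 152.

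The figures reproduce, and 0.95 enters none of them. The only normal quantile used is 1.96, which comes from alpha.

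**Step 2: look for a reading that yields 0.95.**
- *A power term in the same formula.* Replacing 1.96 by 1.96 + 1.645 gives (3.605)² x 0.09 / 0.0025 = 468 for sensitivity, not 138.
- *A test of sensitivity against a fixed value.* The protocol gives no such value. The nulls below are assumptions, shown only to display the range. With 34 NEN patients, true sensitivity 0.90 and an exact one-sided test at 0.025:

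| Assumed null | Reject if true positives at least | Power |
|---|---|---|
| 0.80 | 32 | 0.33 |
| 0.75 | 31 | 0.55 |
| 0.70 | 30 | 0.75 |
| 0.65 | 28 | 0.95 |

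- *The planned kappa test, taken against zero.* At the protocol's inputs the cell proportions are 0.225, 0.025, 0.09 and 0.66. Observed agreement is 0.225 + 0.66 = 0.885. Chance agreement is 0.315 x 0.25 + 0.685 x 0.75 = 0.5925. Kappa = (0.885 − 0.5925) / (1 − 0.5925) = 0.72. With 137 patients the null standard error is 0.0843, so z is about 8.5 and power exceeds 0.999.

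Depending on the hypothesis chosen, the power runs from about 0.3 to nearly 1. It equals 0.95 only for a null of about 0.65, which the protocol does not mention.

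**Step 3: the dropout allowance.**
- Evaluable after 10% loss: 152 x 0.90 = 136.8, of whom 136.8 x 0.25 = 34.2 have NEN.
- Half-width for sensitivity: 1.96 x √(0.09 / 34.2) = 0.1005. At 138 evaluable (34.5 with NEN) it is 0.1001.
- Loss that 152 can absorb while keeping 138: 1 − 138/152 = 0.092, or 9.2%.
- Total that keeps 138 after 10% loss: 138 / 0.90 = 153.3, so 154.

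**The case against.** The best defence is that the line does no work. The sample size comes from 7.1 alone, 7.1 openly states a target margin, and removing the power figure would alter no number, analysis or patient exposure. That is true, and it limits the severity. It does not make the figure correct: the protocol states a design property that it neither derives nor attaches to anything.

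Three stronger readings are tempting, and the document supports none of them.

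- *A reader might infer that the study is underpowered.* The low values in the table rest on nulls that the protocol never names. Without a null, power is undefined rather than low.
- *A reader might infer that nothing is tested, or that nothing in the design could reach 0.95.* Section 7.3 plans a kappa test, and against zero it would exceed 0.95 by a wide margin. The accurate statement is narrower: the 0.95 is tied to no stated hypothesis and played no part in setting the sample size.
- *A reader might set 0.95 against the chance of achieving the planned width.* With 137 evaluable patients, the probability that the half-width is at most 0.10 is 0.52 (Wald) or 0.47 (Wilson). The protocol does not claim 0.95 for this, and a value near one half is normal for any calculation based on expected width. With the full 138 it is 0.52 or 0.48.

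The figure might also be the 95% confidence level entered under the wrong label. That is conjecture, and it would need the same correction.

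On dropout, multiplying by 1.1 is a common convention and the difference is about one evaluable patient. That stands: it is a note, not a material shortfall.

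**Conclusion.** The point holds in a limited form. The power of 0.95 in section 7.2 is unsupported: the calculation in 7.1 is precision-based and has no null, alternative or power term, and no other section supplies a hypothesis. The power is undefined, and the document gives no basis for calling it high or low.

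The dropout slip is real because section 5.3.4 takes lost subjects out of the efficacy analysis. It amounts to two enrolled patients (154 against 152) and a change in half-width from 0.1001 to 0.1005.

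Severity is minor to moderate, because the sample size, the analyses and the endpoints do not depend on the figure. The conclusion about 7.2 rests on the protocol's text and formula and needs no assumed null. The half-widths assume the protocol's own sensitivity of 0.90 and prevalence of 0.25.

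**What to change.** Delete the power figure from section 7.2. State instead that the sample size is based on precision, with an expected 95% confidence interval half-width for sensitivity of about 0.10 from about 34 patients with NEN.

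In section 7.1, keep 152 and restate the dropout allowance as about 9%.

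Both are changes of wording only. They alter no sample size, analysis, endpoint or procedure. The only loss is a claimed assurance that the protocol never derived.

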### 7.3 Statistical Methods

Analysis performed using SPSS 17.0:

Sensitivity, specificity, and positive/negative predictive values calculated via  $2 \times 2$  contingency tables.

ROC curves used to determine AUC and optimal cut-off values (e.g., SUV thresholds).

Kappa test evaluated consistency between 18F-Octreotide PET/CT and pathological diagnoses.

Statistical significance:  $p < 0.05$ .

---

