## Protocol Synopsis

Item	Details
Study Title	18F-Octreotide PET/CT or PET/MR for Diagnosis, Therapeutic Response, and Prognosis in Neuroendocrine Neoplasms

Item	Details
Design	Prospective, single-center, cross-sectional study
Centers	1
Sample Size	152
Indication	Patients with suspected/confirmed NEN
Objective	Evaluate diagnostic efficacy, therapeutic response assessment, and prognostic prediction of 18F-Octreotide PET/CT or PET/MR using pathology as the gold standard.
Primary Endpoint	Completion of multimodal imaging + pathological confirmation
Inclusion Criteria	1. Clinical diagnosis of neuroendocrine neoplasms; 2. Suspected of neuroendocrine neoplasms
Exclusion Criteria	1. Inability to undergo biopsy/surgery. 2. Active malignancy/history within 5 years. 3. Severe uncontrolled comorbidities/active infection. 4. Unable to provide informed consent.
Termination Criteria	1. Study objectives met. 2. Occurrence of SAEs.
18F-Octreotide QC	Produced per Chinese Pharmacopoeia ; passed rodent safety studies; facility holds Type IV Radioactive Pharmaceutical License.
Follow-up Plan	Internal patients: Data extracted from electronic medical records. External patients: Telephone follow-up for pathological results.
Analysis Plan	SPSS 17.0 for: - Sensitivity/specificity/NPV/PPV (2x2 tables) - AUC/optimal SUV cutoff (ROC curves) - Kappa test (imaging vs. pathology concordance) - Significance: p<0.05

Item	Details
Quality Management	AE surveillance system; anonymized data storage; regulatory audit compliance; no identifiable data in publications.

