## 2.2 Research Content

- (1) Primary diagnosis cohort: Multimodal imaging 18F-Octreotide PET/CT or PET-MR + contrast-enhanced CT/MR) followed by biopsy/surgical pathology (gold standard, including grading, Ki-67, SSTR2, TP53/Rb status).
  - (a) Diagnostic efficacy: Calculate sensitivity, specificity, NPV, PPV, AUC-ROC; assess concordance between imaging and pathology.
  - (b) TNM staging: Compare lesion detection rates of 18F-Octreotide imaging vs. CT/MR; evaluate staging accuracy.
  - (c) Tumor heterogeneity: Quantify intratumoral heterogeneity via 18F-Octreotide PET; develop quantitative methods and compare with radiomics for predicting pathological complete response (pCR).
- (2) Recurrence cohort: Post-treatment (surgery/endocrine therapy/chemotherapy) multimodal imaging.

Assess response per PERCIST criteria, explore dynamic imaging parameters for recurrence risk prediction.

Combine radiomics/AI to identify prognostic parameters.

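### Section 7.3 picks an SUV cut-off by ROC in the only cohort and does not say whether the 2x2 tables use it; accuracy reported at that cut-off would be optimistic

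*Protocol*

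**What the plan says.** Section 7.3 lists three analyses. The first is "Sensitivity, specificity, and positive/negative predictive values calculated via" 2x2 tables. The second is "ROC curves used to determine AUC and optimal cut-off values (e.g., SUV thresholds"). The third is a kappa test of PET/CT against the pathological diagnosis. The synopsis has the same list, with the second item given as "AUC/optimal SUV cutoff (ROC curves").

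Section 6.7 gives a criterion that does not depend on the study's own results: uptake exceeding "liver = SSTR-positive malignancy". It also describes pathologic uptake as "Focal uptake in non-physiologic sites", in contrast to diffuse bowel uptake.

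Section 2.2 places accuracy and ROC analysis together in the primary diagnosis cohort: "Diagnostic efficacy: Calculate sensitivity, specificity, NPV, PPV, AUC-ROC; assess concordance between imaging and pathology". Section 5.1 enrols 152 subjects at one center. The protocol mentions no split into training and test subjects, no resampling and no external sample. Section 7.3 does not name the rule that makes a scan positive in the 2x2 tables.

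**The concern.** A cut-off chosen because it best separates diseased from non-diseased subjects in one sample also fits the chance features of that sample. If the same subjects are then tabulated at that cut-off, sensitivity and specificity are on average higher than the cut-off would achieve in new patients. PPV, NPV and kappa come from the same four cells and inherit the excess. The smaller of the two groups suffers most, because fewer subjects there determine where the cut-off falls.

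Section 7.1 plans for a margin of 0.1 around a sensitivity of 0.90. That margin covers sampling error only and makes no allowance for selection of the cut-off. A reader who wanted to use the published SUV threshold would expect more from it than it can deliver. The protocol already holds a criterion free of this problem, but does not tie it to the main accuracy results.

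**Working it through.** **Inputs from the protocol.** Section 7.1: sensitivity 0.90, specificity 0.88, prevalence 0.25, margin 0.1, two-sided alpha 0.05 (z = 1.96), dropout 10%. Section 5.3.4: subjects lost to follow-up are left out of the accuracy analysis.

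**The plan's own figures.**
- Sensitivity: 1.96² × 0.90 × 0.10 / (0.1² × 0.25) = 138.30 (stated 138).
- Specificity: 1.96² × 0.88 × 0.12 / (0.1² × 0.75) = 54.09 (stated 54).
- Dropout: 138 × 1.10 = 151.8, giving 152.

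These reproduce. The sample size matters here only through the group sizes.

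**Group sizes.** 152 × 0.90 = 136.8, about 137 evaluable. At prevalence 0.25, 137 × 0.25 = 34.25, so about 34 with NEN and 103 without. Prevalences of 0.50 and 0.75 were run as well, because inclusion takes both suspected and clinically diagnosed NEN.

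**Assumptions.** The protocol does not define an optimal cut-off; maximising the Youden index J = sensitivity + specificity − 1 was assumed. Scores were taken as normal with equal variance in both groups. The separation that yields 0.90 and 0.88 is d = z(0.90) + z(0.88) = 2.457, which implies AUC = Φ(2.457/√2) = 0.959.

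**Simulation.** In each of 4,000 simulated studies per case, the cut-off was chosen by Youden. Apparent accuracy in that sample was compared with the true accuracy of the chosen cut-off.

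| NEN / non-NEN | Sensitivity: apparent, true, excess | Specificity: apparent, true, excess | Excess in J |
|---|---|---|---|
| 34 / 103 | 0.921, 0.880, +4.1 points | 0.898, 0.885, +1.3 points | +5.4 points |
| 68 / 69 | 0.914, 0.892, +2.2 points | 0.898, 0.876, +2.2 points | +4.4 points |
| 103 / 34 | 0.899, 0.885, +1.3 points | 0.922, 0.880, +4.2 points | +5.5 points |

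Excesses were taken before rounding, so some differ by 0.1 from the rounded columns.

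**Control.** A cut-off fixed in advance at d/2 has true sensitivity and specificity of Φ(1.228) = 0.890. With 34/103 the simulated averages were 0.890 and 0.890, so there is no bias.

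**What this does to PPV, NPV and kappa (34/103, average values put into the table).**
- PPV, apparent: 0.921 × 34 = 31.31 true positives and 0.102 × 103 = 10.51 false positives, so 31.31/41.82 = 0.749. True: 29.92/(29.92 + 11.85) = 0.716.
- NPV, apparent: 92.49/(92.49 + 2.69) = 0.972. True: 91.16/(91.16 + 4.08) = 0.957.
- Kappa, apparent: observed agreement 0.904, chance agreement 0.598, so (0.904 − 0.598)/(1 − 0.598) = 0.76. True: (0.884 − 0.598)/(1 − 0.598) = 0.71.

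**Sensitivity to the assumptions.** Over 137 to 152 evaluable subjects, prevalence 0.25 to 0.75 and AUC 0.77 to 0.96, the excess was 1.3 to 6.4 points in sensitivity, 1.3 to 6.1 in specificity and 4.3 to 8.5 in J. It grows as discrimination weakens.

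**The case against.** The strongest reply is that section 7.3 lists the 2x2 tables, the ROC analysis and kappa as separate items. Nothing says that the tables are built at the ROC cut-off, or that accuracy will be quoted there. Section 8.1 has two physicians read each scan independently, with a senior consultant settling disagreements. A reader call under 6.7 is a natural input to a 2x2 table and to kappa, and on that reading the main results carry no selection bias. This stands, and it makes the point conditional. It does not remove it: 7.3 leaves the input to the tables unnamed, and an optimal cut-off is of little use without its sensitivity and specificity.

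It can also be said that resampling details belong in a statistical analysis plan, and that finding an SUV cut-off by ROC is an ordinary descriptive aim. Both are fair. No fault is found with the ROC analysis itself, or with the absence of resampling details. The open matter is that the protocol sets a data-driven cut-off beside an existing criterion without saying which one defines accuracy.

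Several stronger readings are tempting but unsupported:
- A reader might infer three rival positivity rules. The two statements in 6.7 can be read as successive steps of one visual read, and 7.3 offers the SUV threshold only as an example of ROC output.
- A reader might infer that the planning values 0.90 and 0.88 presuppose a cut-off fixed in advance. Section 7.1 attributes them only to literature, so their basis is unknown.
- A reader might object that a binomial confidence interval would be invalid. The protocol specifies no such interval, only a precision formula.
- A reader might infer that raw SUV is pooled over PET/CT and PET/MR. Section 6.6 does allow reconstruction with "parameters optimized per patient/scanner", but pooling is not stated, 7.3 names PET/CT alone for kappa, and no effect has been quantified.

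**Conclusion.** The point holds in conditional form. The protocol selects an SUV cut-off by ROC in its single cohort, names no other subjects in which to evaluate it, and leaves open whether the 2x2 tables use it. That the cut-off would be scored in the same subjects is inferred from the absence of any others.

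If accuracy is reported uncorrected at that cut-off, the expected excess at the planning values is about 4 points in sensitivity and 1 in specificity with 34/103, about 2 and 2 with 68/69, and about 1 and 4 with 103/34. The largest of these is about 40% of the planned 10-point margin (4.1/10). The upward direction follows from the selection. The size rests on the equal-variance normal and Youden assumptions.

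It would be wrong to conclude that the study's accuracy results as a whole are biased. The AUC is unaffected, and so are 2x2 results under the 6.7 criterion. This is a moderate, inexpensive improvement, not a flaw in the design.

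**What to change.** In section 7.3 and the synopsis:

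1. State that the main 2x2 tables (sensitivity, specificity, PPV, NPV) and kappa use the reader call under the criterion of 6.7, recorded before pathology is known wherever pathology follows the scan.
2. Label the ROC-derived SUV cut-off exploratory, define what makes it optimal, and report its sensitivity and specificity with optimism correction. The bootstrap or cross-validation must repeat the choice of cut-off within each resample.

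An ROC analysis of the lesion-to-liver ratio beside raw SUV is optional.

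The cost is two or three sentences and a little more analysis of images already acquired, with no added subjects or scans. The downside is that accuracy at the optimal cut-off will look a few points lower than an uncorrected figure.

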## 8 Data Recording and Management

### 8.1 Investigator Data Recording

Detailed records of all eligible subjects, including laboratory results.

Two nuclear medicine physicians ( $\geq 5$  years' experience) independently interpret imaging; discrepancies resolved by a senior consultant.

Original data signed and dated by the investigator.

All adverse events (AEs) documented; serious adverse events (SAEs) reported per protocol.

---

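### A kappa test at p<0.05 rejects only chance agreement with pathology, so a significant result does not by itself support a claim of concordance

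*Protocol*

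**What the plan says.** Section 2.2(1)(a) of the protocol lists the diagnostic-efficacy measures for the primary diagnosis cohort and ends with the aim to "assess concordance between imaging and pathology". The only method named specifically for that aim is in section 7.3: "Kappa test evaluated consistency between 18F-Octreotide PET/CT and pathological diagnoses". Section 7.3 closes with a significance level of 0.05 for the section as a whole. The synopsis has the same sequence: "Kappa test (imaging vs. pathology concordance) - Significance: p<0.05".

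Neither place gives a null value for kappa, a smallest acceptable kappa or a confidence interval. The sample size in section 7.1 rests on the precision of sensitivity and specificity, not on kappa. In section 8.1, two physicians "independently interpret imaging; discrepancies resolved by a senior consultant".

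**The concern.** A kappa test with no stated null is ordinarily a test of kappa = 0, that is, of agreement no better than chance. Any scan that carries some information about the diagnosis has a kappa above 0, and a trial of this size will often detect that. A small p-value therefore says little about whether imaging and pathology agree well enough to matter.

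Kappa also treats pathology as one of two interchangeable raters, whereas the protocol makes it the gold standard. Its value depends on the share of patients with NEN as well as on the scan's accuracy. Section 5.3.1 admits both clinically diagnosed and suspected NEN without fixing the split, so the share actually enrolled may differ from the 0.25 used for planning.

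What is at stake is the concordance conclusion alone. If it rested on the p-value, a weak test could be reported as agreeing with pathology.

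**Working it through.** **Inputs from section 7.1:** "Assuming a sensitivity of 0.90, specificity of 0.88, and disease prevalence of 0.25 from literature", "with a margin of error of 0.1", and a two-sided 0.05 level. All other accuracies and NEN shares below are assumptions, shown as a range.

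**The plan's own figures.**
- Sensitivity: 1.96² × 0.90 × 0.10 / (0.1² × 0.25) = 138.3; the plan gives 138.
- Specificity: 1.96² × 0.88 × 0.12 / (0.1² × 0.75) = 54.1; the plan gives 54.
- Dropout: 138 × 1.10 = 151.8; the plan gives 152. If 10% are lost, 152 × 0.90 = 136.8 remain, so about 137 to 138 are evaluable.

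These figures reproduce. None concerns kappa.

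**Kappa from accuracy and share.** Let p be the NEN share, Se the sensitivity and Sp the specificity.
- Scan-positive share: q = p·Se + (1−p)(1−Sp)
- Observed agreement: Po = p·Se + (1−p)·Sp
- Chance agreement: Pe = p·q + (1−p)(1−q)
- Kappa = (Po − Pe)/(1 − Pe)

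At the planning values 0.90/0.88 and p = 0.25: q = 0.315, Po = 0.885, Pe = 0.5925, and kappa = 0.2925/0.4075 = 0.72.

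At 0.50/0.80 and p = 0.25: q = 0.275, Po = 0.725, Pe = 0.6125, and kappa = 0.1125/0.3875 = 0.29.

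**Test of kappa = 0.** The null standard error is √{Pe + Pe² − [p·q(p+q) + (1−p)(1−q)(2−p−q)]} / [(1−Pe)√n].

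For 0.50/0.80 and n = 138 this is √(0.6125 + 0.3752 − 0.8381) / (0.3875 × 11.747) = 0.085. An observed kappa of about 1.96 × 0.085 = 0.17 is then already significant. Across the scenarios below, the threshold lies at about 0.15 to 0.17.

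**Chance of p<0.05 in the positive direction** (n = 138, share 0.25, 200,000 simulated tables per row):

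| Sensitivity/specificity | True kappa | Chance of p<0.05 |
|---|---|---|
| 0.60/0.60 | 0.16 | 54% |
| 0.50/0.75 | 0.23 | 77% |
| 0.60/0.70 | 0.26 | 88% |
| 0.50/0.80 | 0.29 | 91% |
| 0.70/0.70 | 0.33 | 99% |
| 0.90/0.88 (plan) | 0.72 | about 100% |

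The p-value hardly separates the last three rows. The estimate does: 95% of simulated kappas lie between 0.11 and 0.46 for 0.50/0.80, and between 0.58 and 0.84 for 0.90/0.88.

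**Dependence on the NEN share**, with accuracy fixed at 0.90/0.88:

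| Share | 0.10 | 0.25 | 0.50 | 0.75 | 0.80 | 0.90 | 0.95 |
|---|---|---|---|---|---|---|---|
| Kappa | 0.54 | 0.72 | 0.78 | 0.74 | 0.71 | 0.58 | 0.42 |

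For example, at share 0.90: q = 0.822, Po = 0.898, Pe = 0.7576, and kappa = 0.1404/0.2424 = 0.58.

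**The case against.** The strongest reply is that the protocol never makes p<0.05 a success rule for kappa. The line covers the whole of section 7.3, and no claim of agreement resting on it is announced. That is right. A reader might infer a declared decision rule, but the text does not contain one. What stands is that p<0.05 is the only criterion given anywhere for this analysis.

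Secondly, sensitivity, specificity, predictive values and AUC are all planned, and the trial is sized on the first two. A scan with sensitivity 0.50 would show as such in the same 2×2 table. This also stands, and it keeps the point small.

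Thirdly, a CI for kappa and an inter-reader analysis could be in an SAP that is not shown. Their absence is not a fault in itself. The point concerns the test that the protocol does name.

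Four further readings are tempting but not supported:
- That significance is nearly guaranteed for any poor test. At 0.60/0.60 it occurs in only about 54% of trials, and the rates depend on accuracies that are assumed here.
- That case mix makes kappa unusable. Kappa moves little between shares of 0.25 and 0.80, and the only share the protocol states is 0.25.
- That kappa would mislead across cohorts. Section 2.2 sets the concordance aim only for the primary diagnosis cohort, and no comparison of kappas is planned.
- That kappa can say nothing about agreement. An estimate with its interval, read beside accuracy and the NEN share, can.

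**Conclusion.** The point holds in a limited form. The protocol names a kappa test under a p<0.05 line as its specific method for concordance with pathology, and a significant result there does not by itself support a claim of agreement. At about 138 evaluable patients and an NEN share of 0.25, an observed kappa of about 0.15 to 0.17 is enough. Assumed poor tests with true kappas of 0.16 to 0.33 pass in about 54% to 99% of trials. The dependence on case mix is real but matters mainly at high or low shares.

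This rests on reading the kappa test as a test of kappa = 0, which the protocol does not state, and on assumed accuracies other than 0.90/0.88 and shares other than 0.25. The sample size and the main accuracy analyses are unaffected. It is a minor correction to what the trial may conclude about concordance.

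**What to change.** In section 7.3 and the matching synopsis row:
- Remove the p-value as the criterion for kappa.
- Report kappa against pathology as an estimate with a 95% CI, beside the observed NEN share.
- Rest the concordance conclusion on the already planned sensitivity and specificity, each with a 95% CI.

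Optionally, report kappa between the two independent readers, where the measure fits naturally. Section 8.1 does not say that each reader's result before adjudication is kept. If it is not, this option needs a change to data capture as well as to wording.

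The main change needs no extra patients or scans. It costs slightly more reporting, and the trial gives up any statement that agreement was statistically significant.
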